#### ENGAGEMENT WITH HITSYSTEM - INTERVENTION ONLY

38. Nyaka ne ichak dhi e ANC, bende iseyudo sms moro a mora ka oa hospital?

- e. Ooyo, Pok ayudo sms.
- f. Eeh, Aseyudo achiel, to ma ok ngeny ne adek
- g. Eeh, aseyudo kind sms 3 kod 5,
- h. Eeh, Aseyudo sms mohewo 5

39. Bende iseyudo sms moro a moro mapenji wehegi?

- f. Ngeyo kaka idhi.....Yes / No
- g. Manyisi chieng m onego iduogie e hospital..... Yes / No
- h. Maparoni mondo imwony yath..... Yes / No
- i. Maparoni mondo iter nyathi e hospital.....Yes / No
- j. Manyisi mondo idog e hospital mondo inge chal dwako nyathi..... Yes / No

40. Kane I yie ne iyudo sms e no 34, kiyie to dwokie penjo no 36 kaka ne itimo bang yudo sms, ka ok kamano to dhie no 37:

- f. Sms go ne ok okonya.....True / False
- g. Sms ne okonya mondo apar amwony yath.....True / False
- h. Ne an kod chandruok ni ngato nyalo neon sms ma ng'e godo chal mara.....True / False
- i. Sms ne omiya abedo kod e achiel gi hospital/yo thieth.....True / False

- j. Sms ne omiyo anyalo pare chieng ma onego adogie e hospital.....True / False
  - k. Ng'ato ma opgre koda ne osomo sms ma openja.....True / False
  - l. Ja family kata osiepna ne ongeyao chal mara nikech sms no.....True / False
  - m. Sms ne omiya weche mabeyo kaluwore kod thieth mar nyathina.....True / False
  - n. Sms ne omiya mijingo mondo amend dhi mbele kod yudo thieth mar  
PMTCT/EID.....True / False
41. Kiyie to yier seche ma diher ni mondo waparni godo seche ma onega imwony ART
- k. Okadwar,, kik uorna sms
  - l. Pile
  - m. Juma
  - n. Bang juma 2
  - o. Dwe ka dwe

Erokamono ahinya kuom miyowa saa mari kod duoko penjo.

## Appendix IIC. 6 Month Postpartum survey (Intervention and Control Sites)

### For interviewer to fill out:

Study ID: \_\_\_\_\_

Date of interview \_\_\_\_\_

Interviewer initials \_\_\_\_\_

Partner status & Disclosure

1. **Kit keny mari en mane?**
  - a. Pok adhi katedo
  - b. Ose kenda
  - c. Pok okenda to an an kod jaherana
  - d. Wapogore kod jaherana
  - e. Wawere kod jaherana
  - f. An Chi liel
2. Dak mari chal nade?
  - a. Aonge jaherana sani
  - b. Adak mopogore kod jaherana
  - c. Adak kamoro achiel kod jaherana
3. Chal mari mar ayaki isenyiso ng'a?
  - a. Onge ng'ato ma asenyiso
  - b. Jaoda/jaherana
  - c. Ng'ato achiel kase anyuola
  - d. Ng'ato achiel kase osiepni
  - e. Ng'ato achiel kose janyuolni
4. Chal mar ayaki mar jaherani?
  - f. En kute mag ayaki
  - g. Oonge kod kute mag ayaki
  - h. Ok Ong'ere
  - i. Aonge jaherana sani
5. Jaherani ma sani e wuon nyathi? ..... Eeh / ooyo/ NA
6. En ng'a ma chiwo yore kaka onego uti kod pesa e odu?
  - a. Jaherana, seche duto
  - b. Jaherana ngenyne ma oloya
  - c. Jaherana kod an maromre
  - d. An ngenyne molooyo jaherana
  - e. An, Seche duto.
  - f. Aonge jaherana sani
7. Yuto maru e juma?
  - a. Tin ne mia 500
  - b. Kind mia 500-750
  - c. Kind mia 750-1,000
  - d. Kind 1,000-2,500
  - e. Oingo 2,500
8. Chunya chandre nikech aonge pesa moromo ma anyalo chopo godo hospital kata ma nyathina nyalo yudo godo thieth?
  - a. Ayiego Ahinya
  - b. Ayiego
  - c. Adagi
  - d. Adagi Ahinya

Partner Support (To be filled at 6 month VL test)

9. Nyaka ne i nyuol bende jaherani ose chung kodi e yore gi?:

|   | Podi | Tinne | Seche moko | Pile pile |
|---|------|-------|------------|-----------|
| 9a. Dhi e thieth mar nyathi sama dwarore?             |      |       |            |           |
| 9b. Miya pesa mar dhi godo hospital?                  |      |       |            |           |
| 9c. Miya paro kaka inyalo pidho nyathi kata keto ler? |      |       |            |           |
| 9d. Konyi kod tije ot mondo iyue?                     |      |       |            |           |
| 9e. Paroni mondo imi nyathi yath?                     |      |       |            |           |
| 9f. Paroni mond imwony yath?                          |      |       |            |           |
| 9g Paroni mondo iluw thieth kaka daktari ne owacho?   |      |       |            |           |
| 9h.Miya pesa mar nyiew yath kata vitamins?            |      |       |            |           |
| 9i. Chiwo mij'ingo mondo l dag e ngima maber?         |      |       |            |           |
| 9j. Lemo kanyakla mondo ubed kod ngima maber?         |      |       |            |           |

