**Statistical analyses for objective 1 (complete retention).** Data from women who have a documented reason for incomplete care at the study hospital (e.g. transfer facility, pregnancy loss, maternal death) will not be included in analyses. To demonstrate the efficacy of HITSytem 2.1 versus SOC, we will test for differences between arms by modeling complete PMTCT as a function of study arm and selected covariates (e.g., age, partner support, depression) using logistic mixed models with a random site intercept (to adjust for clustering). In post hoc analyses we will explore patient and facility-level characteristics as potential moderators of the effect of HITSytem 2.1, and examine changes in key individual level factors (disclosure status, partner status, depression, partner support) at the midpoint (delivery) and again at the end (6m postpartum). To assess mediating factors, we will compute average levels of provider knowledge and motivation for each site at baseline and end of study. These knowledge and motivation scores, as well as patient knowledge and motivation levels, will be compared pre-post intervention and between study arms to assess change within and between sites. In addition, provider and patient knowledge and motivation will be examined as predictors of PMTCT completion using logistic regression.

[figure not shown]

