#### Partner Support

12. How often during your pregnancy did your male partner support you in the following ways:

|  | Never | Rarely | Sometimes | Often |
|--|-------|--------|-----------|-------|
| 12b. Provided money for transport to the hospital?   |       |        |           |       |
| 12c. Gave you advice on remaining healthy while pregnant?                                    |       |        |           |       |
| 12d. Helped you with household responsibilities so that you could rest?                      |       |        |           |       |
| 12e. Helped you with household responsibilities so that you could attend PMTCT appointments? |       |        |           |       |
| 12f. Reminded you to take your medication  |       |        |           |       |
| 12g. Reminded you of the importance of following doctor's instructions.                      |       |        |           |       |
| 12h. Provided money to purchase medication or vitamins?                                      |       |        |           |       |
| 12i. My husband gave me encouragement throughout my pregnancy                                |       |        |           |       |
| 12j. Me and my husband prayed together for a safe pregnancy and delivery                     |       |        |           |       |

13. Did your partner attend any PMTCT appointments with you?
- a. No, he did not attend any
  - b. He attended 1
  - c. He attended 2
  - d. He attended 3 or more.
  - e. N/A, no partner.
14. If #13 was no, what were the reasons he did not attend?
- a. He was working during my PMTCT appointments \_\_\_\_\_ Yes / No
  - b. He lives or works far away \_\_\_\_\_ Yes / No
  - c. He felt unwelcomed/uncomfortable at the clinic \_\_\_\_\_ Yes / No
  - d. I did not want him to attend \_\_\_\_\_ Yes / No
  - e. He did not want to attend \_\_\_\_\_ Yes / No
  - f. He had other responsibilities \_\_\_\_\_
  - g. Other, please specify \_\_\_\_\_
15. Did your male partner provide support for your child's delivery? Please select the most accurate answer.
- a. I do not have a male partner
  - b. No, my male partner did not provide any type of support for my child's delivery.
  - c. My male partner provided funding for me to get to the hospital, but did not come himself.
  - d. My male partner escorted me to the hospital while I was in labor.
  - e. My male partner visited me in the hospital after my child was born.

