### Partner Support (To be filled at 6 month VL test)

9. How often since your infant's birth has your male partner supported you in the follow ways:

|  |       |        |           |            |
|--|-------|--------|-----------|------------|
|  | Never | Rarely | Sometimes | Frequently |
|--|-------|--------|-----------|------------|

|  |  |  |  |  |
|--|--|--|--|--|
| 9a. Attended your child's medical appointments?                        |  |  |  |  |
| 9b. Provided money for transport to the hospital?                      |  |  |  |  |
| 9c. Gave you advice on infant feeding or hygiene?                      |  |  |  |  |
| 9d. Helped you with household responsibilities so that you could rest? |  |  |  |  |
| 9e. Reminded you to give your child medication?                        |  |  |  |  |
| 9f. Reminded you to take your medication?                              |  |  |  |  |
| 9g. Reminded you of the importance of following doctor's instructions? |  |  |  |  |
| 9h. Provided money to purchase medication or vitamins?                 |  |  |  |  |
| 9i. Provide encouragement to live a healthy life?                      |  |  |  |  |
| 9j. Pray together for the health of your family?                       |  |  |  |  |

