### Depression

Kiyie to yier dwoko machiegni gi kaka ne iwinjo kuom ndalo 7 mosekalo,ok kawuono kende.

23. Ase ngiyo mbele kod mor mar gik mangeny
  - e. Kaka asebedo ga katimo
  - f. Matin kaka asebedo katimo
  - g. Matin ahinya molooyo kaka asebedo
  - h. Ak asebedo
24. Weche ka odhi marach to asebedo ka ajilaumu
  - e. Eeh, Ngenyne
  - f. Eeh , seche moko
  - g. Ok seche te
  - h. Ooyo, podi
25. Asebedo ka awinjo ka aluor ma onge gima omiyo
  - e. Eeh,seche mangeny
  - f. Eeh, seche moko
  - g. Ooyo, ok ahinya
  - h. Ooyo,podi
26. Asebedo ma ok amor, ma asebedo ka aywak
  - e. Eeh, seche mangeny
  - f. Eeh, seche moko
  - g. Mana seche moko
  - h. Ooyo,podi
27. Paro mar hinyruok an awuon ase bedogodo
  - i. Eeh, Ngenyne
  - j. Seche moko
  - k. Mana seche moko
  - l. Podi

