#### Partner Support

12. Ndalo mane iyach jaherani ma dichwo bende nekonyi e yore gi, kaka?:

|  | Podi | Ok ahinya | Seche moko | Ngenyine |
|--|------|-----------|------------|----------|
| 12b. Miya pesa ma iting'i godo ka idhi e od thieth?                                  |      |           |            |          |
| 12c. Miya paro kaka inyalo bedo gi ngima maber ndalo ma iyach?                       |      |           |            |          |
| 12d. Konyi kod tije mag ot mondo iywe?   |      |           |            |          |
| 12e. Konyi kod tije mag ot mondo idhi e thieth mar PMTCT?                            |      |           |            |          |
| 12f. Paroni mondo imwony yath.   |      |           |            |          |
| 12g. Paroni mondo iluw thieth kaka daktari ne owacho.                                |      |           |            |          |
| 12h. Miya pesa mar nyiew yath kata vitamins?   |      |           |            |          |
| 12i. Chuora ne omiya mijingo ndalo mane a yach                                       |      |           |            |          |
| 12j. An kod chuora ne walemo kanyakla mondo atiek ich maber kendo mondo anyuol maber |      |           |            |          |

13. Bende ne udhi kod jaherani e thieth mar PMTCT kamoro achiel?
- a. Ooyo, ne ok odhi kat achiel
  - b. Ne odhi dichiel
  - c. Ne odhi diriyo
  - d. Ne odhi molooyo adek.
  - e. Aonge jaherana.
14. Ka #13 en Ooyo, en ang'o momiyi ne ok odhi?
- a. Ne entie e tich seche mane adhi e PMTCT \_\_\_\_\_ Eeh / Ooyo
  - b. Odak kendo otiyo mabor \_\_\_\_\_ Eeh / Ooyo
  - c. Chunya ne ok orwako bedo e od thieth \_\_\_\_\_ Eeh / Ooyo
  - d. Ne ok adwar ni mondo odhi \_\_\_\_\_ Eeh / Ooyo
  - e. Ne ok odwar dhi \_\_\_\_\_ Eeh / Ooyo
  - f. Ne en kod tije mamoko \_\_\_\_\_ Eeh / Ooyo
  - g. Mamoko, ler ane \_\_\_\_\_
15. Be jaherani madichwo ne okonyi sama ne idhi nyuol? Kiyie to yier dwoko miyiego.
- g. Aonge kod jaherana madichwo
  - h. Ooyo, Jaherana ma dichwo ne ok ochiwo kony moro a mora seche mane adhi nyuol.
  - i. Jaherana ma dichwo ne okonya kod pesa mar chopo hospital, ento ne ok ochopo.
  - j. Jaherana ne okowa e hospital seche mane muoch kaya.
  - k. Jaherana ne obiro nena e hospital bang ka ose nyuol nyathi.
  - l. Jaherana ne okowa e hospital seche mane muoch kaya kendo ne obiro nena e hospital bang ka ose nyuol nyathi

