#### Risk of Violence

Kuom weche gi chakre (19-22), ), yier duoko manyiso kaka gik moko osetimre kuom dweche 12 mosekalo.

|  | Podi | Ok Ahinya | Seche Moko | Ngenyne |
|--|------|-----------|------------|---------|
| 21. Kuom dweche 12 mosekalo, be jaherani ose yanyi kata miyi mondo iwinj marach ne in iwuon? |      |           |            |         |
| 22. Kuom dweche 12 mosekalo , be jaherani ose goyi, gweyi,ywayi piny kata rodhi?             |      |           |            |         |
| 23. Kuom dweche 12 mosekalo , be jaherani ose goyo, gweyo,ywayo piny kata rodho nyathini?    |      |           |            |         |
| 24. Kuom dweche 12 mosekalo, be jaherani osechuni mondo uriwru kode to ne ok idwa.?          |      |           |            |         |

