### Depression

Kiyie to yier dwoko machiegni gi kaka ne iwinjo kuom ndalo 7 mosekalo,ok kawuono kende

10. Asebedo gi geno kod ilo ne gik moko
  - a. En mangey kaka ase timo
  - b. Matin ahinya kaka asetimo
  - c. Matin moromo
  - d. Ok asebedo
11. Weche ka odhi marach to asebedo ka ajilaumu
  - a. eeh seche te
  - b. seche moko
  - c. ok seche te
  - d. ooyo podi
12. Asebedo ka awinjo ka aluor ma onge gima omiyo
  - a. Eeh,seche mangeny
  - b. Eeh, seche moko
  - c. Ooyo, ok ahinya
  - d. Ooyo,pod
13. Asebedo ma ok amor, ma asebedo ka aywak
  - a. Eeh, seche mangeny
  - b. Eeh, seche moko
  - c. Mana seche moko
  - d. Ooyo,podi
14. Paro mag hinyruok an awuon ase bedogodo
  - a. Eeh, Ngenyne
  - b. Seche moko
  - c. Mana seche moko
  - d. Podi

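### In the Luo surveys, answer labels for partner support, violence and depression change between delivery and 6 months, so part of any measured change may come from the form

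*Combined protocol and SAP*

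**What the plan says.** The paragraph on participant surveys (Procedures and Data Management) lists partner support, depression and risk of violence among the patient-level measures. It says the surveys after delivery and at 6 months repeat them, so that changes which may mediate or moderate the intervention effect can be assessed. The statistical analyses for objective 1 then plan, post hoc, to "examine changes in key individual level factors (disclosure status, partner status, depression, partner support", among others, at delivery and again at 6 months. Violence is not in that list.

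The Luo forms print these answer scales:

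- Delivery (Appendix IIB), partner support item 12: "Podi | Ok ahinya | Seche moko | Ngenyine".
- Delivery, risk of violence: "Podi | Ok Ahinya | Seche Moko | Ngenyne". The enrollment form (Appendix IIA) uses the same violence labels.
- 6 months (Appendix IIC), partner support item 9 and risk of violence: "Podi | Tinne | Seche moko | Pile pile".
- Depression, enjoyment item: the third answer at enrollment and delivery is "Matin ahinya molooyo kaka asebedo"; the second answer at 6 months is "Matin ahinya kaka asetimo".

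**The concern.** A change score is interpretable only if the same state draws the same answer at both visits. If the label for the top category becomes more or less demanding, a woman whose circumstances have not altered may tick a different box. If an answer phrase moves to another position, a position-based score may move with it. Either would appear as change in support, violence or mood. Because each translation drifts in its own way, the effect could also pass for a difference between Siaya and the Coast sites. What is at stake is the descriptive change analysis and any moderator or mediator work that draws on these measures.

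**Working it through.** The plan states no figure on this point, so the check is a label-by-label comparison, followed by exposure arithmetic and an illustration of size.

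**1. Frequency grids.** Between Luo delivery and Luo 6 months the first label (*Podi*) and the third (*Seche moko*) stay. The second goes from *Ok ahinya* to *Tinne*, and the fourth from *Ngenyine* (also spelled *Ngenyne*) to *Pile pile*. That is two of four labels, in both grids.

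**2. Is the change in the source?**

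- Violence: no. The English grid is "Never | Rarely | Sometimes | Frequently" at all three surveys, so the change arises in the Luo translation alone.
- Partner support: partly. English goes from "Never | Rarely | Sometimes | Often" at delivery to "Never | Rarely | Sometimes | Frequently" at 6 months.
- The Swahili forms keep their top label from delivery to 6 months in both grids.

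**3. What does the new top label mean?** In the SMS-frequency items (Luo IIB item 41, Luo IIC item 38), *Pile* is the answer for *daily*. In the viral load items of Luo IIC (items 31 to 34), *pile* renders *routine*. In the same 6-month form, *Ngenyne* still stands for *often* in the self-harm item. The form thus uses both words, but the strength of *Pile pile* relative to *Ngenyine* is not settled by the text.

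**4. Depression.** The English options are the same at all three surveys. In Luo, *Matin ahinya* sits in the third enjoyment answer at enrollment and delivery and in the second at 6 months. The third answer becomes *Matin moromo*, and the stem is reworded. The top self-blame answer goes from *Eeh, Ngenyne* at delivery to *eeh seche te* at 6 months.

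**5. Exposure.** Table 2 places 4 of 6 matched pairs in Siaya, that is 8 of 12 sites, 4 per arm. The documents give no language split, so Luo use in Siaya is an assumption.

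- As first planned: 8 × 96 = 768 of 12 × 96 = 1,152, or 67%.
- After the extension: total 1,152 + 10 × 30 = 1,452. Depending on whether two, one or none of the two closed sites are in Siaya, the count is 768 + 30 × 6 = 948, 768 + 30 × 7 = 978 or 768 + 30 × 8 = 1,008. That is 65%, 67% or 69%.

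**6. Illustration of size.** No scoring rule or answer distribution is given, so every input here is assumed. Code answers 0 to 3 by position.

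- Frequency item: fall in mean = share in the top category × share who drop one step because of the label. With 10% to 50% and 25% to 100%, the range is 0.10 × 0.25 = 0.025 to 0.50 × 1.00 = 0.50 per item. This assumes the new label is the more demanding one. It ignores the changed second label.
- Enjoyment item: if 5% to 30% choose the *Matin ahinya* answer at both visits and it moves one position, the item mean falls by 0.05 to 0.30, which would look like improvement.

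A range from 0.025 to 0.50 on a 0-to-3 item runs from trivial to material. It shows only that the effect cannot be dismissed.

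**The case against.** A reader might infer that *often* became *daily*, so that the Luo forms must show falling support and less violence. The documents do not support that. *Pile* also renders *routine*, and *Pile pile* appears only in the place of the English *Frequently*. A Luo speaker must judge its strength.

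Nor can it be said that an identical depression answer takes a new score. The two enjoyment phrases share *Matin ahinya* but are not the same phrase. Trained mentor mothers also administer the surveys, which may soften reliance on a printed word.

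Partner support is not like-for-like in any language. The English top label changes, the reference period moves from pregnancy to the time since birth, some items differ, and enrollment asks about importance and expectation rather than frequency. Swahili drifts too: its lowest violence label differs between delivery and 6 months, and some depression options are reworded.

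The change analysis is post hoc, and the mediation that is specified in detail concerns knowledge (information) and motivation.

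All of this stands and limits the claim. It does not remove the mismatch: for violence and depression the English options are constant and the Luo ones are not, although the protocol treats the measures as the same.

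**Conclusion.** The concern holds in limited form. Luo answer labels for partner support, violence and two depression items differ between delivery and 6 months, so part of any change seen in Luo respondents may come from the form. The direction is open until the form is back-translated, and the size cannot be derived from the documents; the point shifts above are illustrations that rest on assumed coding and answer shares.

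Exposure is up to 8 of 12 sites, if Luo is used in Siaya. It would be wrong to read this as a bias in the trial's main result. Siaya sites are matched 4 against 4, both arms use the same forms, and neither primary outcome is taken from these scales. Partner support and depression are named as example covariates for the Objective 1 model; enrollment values would avoid the 6-month shift. The point should be acted on because the remedy is cheap and the planned change analyses depend on it.

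**What to change.** **Forms.** Back-translate the Luo 6-month survey. Align its violence, support and depression labels and its option order with the Luo delivery form. Record form language and version for every survey, since a mid-study correction leaves two 6-month versions in the data. Ten sites were still enrolling when the extension was written, so at least six of the eight Siaya sites had 6-month surveys ahead.

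**Analysis rule for 6-month forms already completed.**

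- Analyse change within language and form version.
- Code violence and the support items common to both surveys as never/any, as the main or sensitivity coding. *Podi* is unchanged, so this is the most stable cut, though the label next to it did change.
- Leave the enjoyment item out of Luo depression change scores, and add a sensitivity analysis that also omits self-blame.

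**Cost.** One reprinted form, two form versions to track, a short addition to the analysis plan, and some detail lost by collapsing categories.

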### Depression

Kiyie to yier dwoko machiegni gi kaka ne iwinjo kuom ndalo 7 mosekalo,ok kawuono kende

10. Asebedo gi geno kod ilo ne gik moko
  - a. En mangey kaka ase timo
  - b. Matin ahinya kaka asetimo
  - c. Matin moromo
  - d. Ok asebedo
11. Weche ka odhi marach to asebedo ka ajilaumu
  - a. eeh seche te
  - b. seche moko
  - c. ok seche te
  - d. ooyo podi
12. Asebedo ka awinjo ka aluor ma onge gima omiyo
  - a. Eeh,seche mangeny
  - b. Eeh, seche moko
  - c. Ooyo, ok ahinya
  - d. Ooyo,pod
13. Asebedo ma ok amor, ma asebedo ka aywak
  - a. Eeh, seche mangeny
  - b. Eeh, seche moko
  - c. Mana seche moko
  - d. Ooyo,podi
14. Paro mag hinyruok an awuon ase bedogodo
  - a. Eeh, Ngenyne
  - b. Seche moko
  - c. Mana seche moko
  - d. Podi

### Risk of Violence

Kuom weche gi chakre (15-18), yier duoko manyiso kaka gik moko osetimre kuom dweche 12 mosekalo?

|  | Podi | Tinne | Seche moko | Pile pile |
|--|------|-------|------------|-----------|
| 15. Kuom dweche 12 mosekalo, be jaherani ose yangi kata miyi mondo iwinj marach ne in iwuon? |      |       |            |           |
| 16. Kuom dweche 12 mosekalo , be jaherani ose goyi, gweyi,ywayi piny kata rodhi?             |      |       |            |           |
| 17. Kuom dweche 12 mosekalo , be jaherani ose goyo, gweyo,ywayo piny kata rodho nyathini?    |      |       |            |           |
| 18. Kuom dweche 12 mosekalo, be jaherani osechuni mondo uriwru kode to ne ok idwa?           |      |       |            |           |

